## 1.2. Specific Aims

**Primary Aim:** Determine the effectiveness of prophylactic NPWT in reducing the rate of SSIs after cesarean in obese women. *We hypothesize that obese women will have lower rates of SSIs after cesarean with use of prophylactic NPWT than with standard care.*

**Secondary Aim#1:** Assess the safety of prophylactic NPWT in obese women as measured by frequency of adverse events including skin blisters, allergic skin reactions, and wound bleeding. *We hypothesize that the rate of adverse events will not be significantly higher with use of prophylactic NPWT than with standard care.*

**Secondary Aim#2:** Evaluate the cost-effectiveness of prophylactic NPWT compared with standard wound dressing in obese women as measured by the incremental cost per case of SSI prevented and per quality-adjusted life year (QALY). *We hypothesize that prophylactic NPWT in obese women at cesarean will be cost-effective.*

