## **2.3. Cost-benefit of Prophylactic NPWT**

The current FDA-cleared prophylactic single-use NPWT devices cost between \$200 (PICO™) and \$500 (Prevena™) per unit and are increasingly being used after cesarean. Given the cost, prophylactic NPWT must be shown in an independent, suitably powered, high-quality trial to improve clinical outcomes to justify widespread use. However, if proven to be effective at reducing SSIs after cesarean, use of the device may not only be cost-effective, but cost-saving. Two cost-effectiveness analyses of prophylactic NPWT have recently been published suggesting that use prophylactic NPWT after cesarean may be cost effective under a range of conditions. However, because data on its

effectiveness at cesarean are lacking, the cost-effectiveness analyses were based on data extrapolated from other surgical procedures. In addition to the effectiveness data this trial will produce, the accompanying cost-effectiveness analysis will aid decision-making on general clinical use.

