### **5.3. Data Processing**

The Data Management Center (DMC) at Washington University School of Medicine will be responsible for data management and analysis in accordance with the analysis plan to be finalized by the steering committee and approved by the DSMB. The Data Management Team based at Washington University includes an experienced statistician and a database manager. Each site PI and nurse coordinator will be responsible for liaison with the DMC including transmitting de-identified abstracted information contained in the data collection forms. Data management at each site will include: procedures for data entry, data editing, and compilation; procedures for data transmittal; and procedures for quality control, data verification, confidentiality and security. Data will be collected and managed with REDCap (Research Electronic Data Capture), an established, secure, web-based data capture and management tool developed at Vanderbilt University and supported by the bioinformatics team at WUSM (<http://www.biostat.wustl.edu/redcap/>). The security of the database will be maintained by the use of dedicated password protected encrypted computers with multiple private backups (daily, weekly, and monthly including on- and off-site storage for protection against disaster).

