## **6. Data Analysis**

### **6.1. Sample Size and Power**

#### **6.1.1. Primary Aim – Effectiveness**

The total sample size for the trial is estimated based on the primary outcome. We then estimate, on the basis of the sample size for the primary aim, the power we will have to detect clinically significant differences in the secondary aims. All sample size and power estimates are based on two-tailed tests, enabling us to detect an increase or decrease in rates of outcomes with use of prophylactic NPWT.

The baseline rate of SSIs in obese women from our preliminary data is 11.6%. Furthermore, rates of SSIs at the study sites in all women range from 6 to 12% and are expected to be higher in obese women. Assuming a conservative baseline rate of 10%, we estimate that a total of **2850** subjects (1425 NPWT and 1425 standard care) will be sufficient to detect a 30% relative difference in SSIs, with 80% power and 5% significance level and

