**Table 4: Sample size estimation**  
(Power=80%, 2-tailed,  $\alpha =0.05$ )

Detectable relative difference	Anticipated SSI rate with NPWT (assuming 10% baseline rate)	Sample size (assuming 5% loss to follow-up)
50%	5.0%	910
40%	6.0%	1514
33%	6.7%	2316
30%	7.0%	2850
25%	7.5%	4215
20%	8.0%	6760

accommodation of 5% loss to follow-up (Table 4). This 30% difference represents the difference between a 10% rate of SSI in the standard care group and a 7% rate in the NPWT group.

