**Effectiveness:** The effectiveness measures will be rate of SSI and QALYs. We will calculate QALYs by applying utility weights (1=perfect health, 0=death) to various health states values derived from the EuroQol five dimensions questionnaire (**EQ-5D**). The EQ-5D is a standardized instrument for measuring generic health status. The health status measured with EQ-5D-3L is used for estimating preference weight for that health status, then by combining the weight with time, QALYs can be computed. We will administer the EQ-5D to patients at the 30-day follow-up phone call. Once the data have been collected a scoring function can be used to assign a value (i.e., EQ-5D™ index score) to self-reported health states from a set of U.S.-generated value set (preference weights).

EQ-5D is one of the most commonly used generic health status measurement, and its good validity and reliability have been reported in various health conditions. The EQ-5D-3L questionnaire is made up for two components; health state description and evaluation. In the description part, health status is measured in terms of five dimensions (5D); *mobility, self-care, usual activities, pain/discomfort, and anxiety/depression*. Mobility dimension asks about the person's walking ability. Self-care dimension asks about the ability to wash or dress by oneself, and usual activities dimension measures performance in "work, study, housework, family or leisure activities". In the pain/discomfort

dimension, it asks how much pain or discomfort they have, and in the anxiety/depression dimension, it asks how anxious or depressed they are. The respondents self-rate their level of severity for each dimension using a three-level (3L) scale: *having no problems, having some or moderate problems, being unable to do/having extreme problems*. In the evaluation part, the respondents evaluate their overall health status using the visual analogue scale (EQ-VAS) which ranges from 0 (the worst health you can imagine) to 100 (the best imaginable health state).

**Cost-effectiveness:** The measures of cost-effectiveness of prophylactic NPWT will be incremental cost per case of SSI prevented and incremental cost per QALY. They will be calculated as follows.

Incremental cost per case of SSI prevented:

$(\text{Mean Cost}_{\text{Prophylactic NPWT}} - \text{Mean Cost}_{\text{standard care}}) \div (\text{Mean SSI Rate}_{\text{Prophylactic NPWT}} - \text{Mean SSI Rate}_{\text{standard care}})$

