Incremental cost per QALY:

$(\text{Mean Cost}_{\text{Prophylactic NPWT}} - \text{Mean Cost}_{\text{standard care}}) \div (\text{Mean QALY}_{\text{Prophylactic NPWT}} - \text{Mean QALY}_{\text{standard care}})$

All estimates of costs, outcomes, and cost-effectiveness will be reported as means with 95% confidence intervals. In accordance with the current threshold used in the U.S., prophylactic NPWT will be considered cost-effective if the incremental cost per QALY is less than \$100,000^62. We will conduct sensitivity analysis to evaluate uncertainty of the results by varying probability (e.g., baseline rate of SSI, magnitude of risk reduction) and cost parameters (e.g., cost of the NPWT device, healthcare cost). We will employ Monte Carlo simulation to assess the robustness of our findings by simultaneously sampling distributions of multiple parameters within the model.

*Etiology, timing, and risk factors of SSIs in obese women*

For these analyses, the two study groups (NPWT and standard care) will be combined into a cohort, and all analyses will adjust for group assignment and study site. We will evaluate wound culture data to determine the types and frequency of different bacteria including MRSA. We will use time-to-event analyses to estimate median time to SSIs and time to heal. We will identify risk factors

for SSI initially based on factors associated with SSI in bivariate analysis (at  $P<0.1$  threshold), biological plausibility, and factors reported in the literature. We will use backwards elimination to reduce the number of variables in the model. Variables that are significant will be retained as risk factors for SSIs in obese women. Fit for the final model will be assessed by using the Hosmer-Lemeshow goodness-of-fit test.

*Other planned secondary analysis*

- Effect of prophylactic negative pressure wound therapy on a composite of any wound complication
- Effect of prophylactic negative pressure wound therapy on rate and type of wound cultures
- Effect of prophylactic negative pressure wound therapy on healthcare resource utilization
- Association between levels of cefazolin in the subcutaneous layer before fascial incision and after fascial closure and risk of surgical site infection
- Risk of surgical site infection and other wound complications with different skin incision types
- Relationship between skin microbiome at the incision site and risk of surgical site infection

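### Two rules for the cost-effectiveness aim are wrong as written: cost per SSI prevented has a reversed denominator, and the $100,000-per-QALY threshold has no sign condition

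*Combined protocol and SAP*

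**What the plan says.** Secondary Aim 2 (section 1.2) assesses cost-effectiveness "as measured by the incremental cost per case of SSI prevented and per quality-adjusted life year (QALY"). Section 6.2.2, under Cost-Effectiveness Analysis, then gives the formulas:

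- The "incremental cost per case of SSI prevented" is mean cost (NPWT minus standard care) divided by mean SSI rate, also taken as NPWT minus standard care.
- The incremental cost per QALY has the same numerator, divided by mean QALYs, NPWT minus standard care.

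The decision rule follows: "prophylactic NPWT will be considered cost-effective if the incremental cost per QALY is less than" $100,000. The section also plans 95% confidence intervals, sensitivity analyses and Monte Carlo simulation, and commits to published guidance on economic evaluation alongside trials. Nothing in it says how a result is classified when NPWT yields fewer QALYs, or when one arm is better on both cost and effect.

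Section 2.3 anticipates that "if proven to be effective at reducing SSIs after cesarean, use of the device may not only be cost-effective, but cost-saving".

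**The concern.** The two points are separate.

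SSIs prevented by NPWT are the standard-care rate minus the NPWT rate. The printed denominator is the opposite difference. The order that is right for QALYs, where more is better, has been used for an outcome where more is worse. The cost saving that section 2.3 hopes for would be reported as a positive cost, and a costlier device that increased infections would show an ordinary positive cost per SSI prevented.

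A threshold on a cost-effectiveness ratio has its usual meaning only when the effect difference is positive. A negative ratio can mean cheaper and better, or dearer and worse, and the printed rule passes both. This is the only stated decision rule for Secondary Aim 2, so at stake is a declaration of cost-effectiveness for a device that is worse on both axes.

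**Working it through.** **Inputs.** SSI rates are "the difference between a 10% rate of SSI in the standard care group and a 7% rate in the NPWT group" (section 6.1.1, Table 4). The device price is $500 (section 2.3), used as the cost difference with no offsets. The threshold is $100,000 per QALY and the horizon 30 days (section 6.2.2). The plan gives no expected cost or QALY differences, so the other values below are assumptions; the sign results do not depend on their size.

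**The plan's own figure.** The plan prints no cost-effectiveness result to reproduce. Its design rates do reproduce its sample size: 10% versus 7%, two-sided 5%, 80% power gives 1,356 per arm, 2,712 in total, and 2,712 / 0.95 = 2,855, against 2,850 stated.

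**Step 1: cost per SSI prevented.** Printed: cost difference / (NPWT rate - standard-care rate). Correct: cost difference / (standard-care rate - NPWT rate).

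| Cost difference | NPWT vs standard care | Printed | Correct |
|---|---|---|---|
| +$500 | 7% vs 10% | 500 / (-0.03) = -$16,667 | +$16,667 |
| -$100 (assumed) | 7% vs 10% | -100 / (-0.03) = +$3,333 | -$3,333 |
| +$500 | 11% (assumed) vs 10% | 500 / 0.01 = +$50,000 | -$50,000 |

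In the last row NPWT adds one SSI per 100 women and prevents none. The sign is wrong in every row; the magnitude is right.

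**Step 2: the QALY rule.** Let dC and dQ be the cost and QALY differences, NPWT minus standard care. The printed rule is dC/dQ < 100,000. Net monetary benefit is NMB = 100,000 x dQ - dC. For dQ > 0 the printed rule is equivalent to NMB > 0. For dQ < 0, multiplying through by dQ reverses the inequality, so the rule passes exactly when NMB < 0.

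| dC | dQ | Ratio | Printed rule | NMB |
|---|---|---|---|---|
| +$500 | +0.01 | $50,000 | pass | +$500 |
| -$500 | +0.002 | -$250,000 | pass | +$700 |
| +$500 | -0.002 | -$250,000 | pass | -$700 |
| +$400 | -0.0002 | -$2,000,000 | pass | -$420 |
| -$10 | -0.001 | $10,000 | pass | -$90 |
| -$400 | -0.001 | $400,000 | fail | +$300 |
| +$400 | +0.001 | $400,000 | fail | -$300 |

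Rows 2 and 3 share one ratio although one is the best kind of result and the other the worst. Rows 6 and 7 share another with opposite net benefits. The ratio alone cannot decide.

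**Step 3: could the QALY difference come out negative?** Over 30 days, one full unit of utility is 30/365 = 0.082 QALY. Assume an SSI lowers utility by 0.1 throughout. The 3-point SSI reduction is then worth 0.03 x 0.1 x 0.082 = 0.00025 QALY per woman. Assume an EQ-5D standard deviation of 0.15, with 1,425 x 0.95 = about 1,354 women per arm. The standard error is 0.15 x 0.082 x sqrt(2/1,354) = about 0.0005. The estimated difference would then be negative about 30% of the time even if NPWT achieves its design effect. For utility losses of 0.1 to 0.2 and standard deviations of 0.10 to 0.20, the range is about 6% to 35%.

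**Step 4: effect on simulation output.** Suppose the printed rule is applied to each Monte Carlo draw, with dC normal (mean $300, SD $100) and dQ normal (SD 0.002, wider than in Step 3; all assumed).

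| Mean dQ | Printed rule passes | NMB > 0 |
|---|---|---|
| +0.001 | 49% | 19% |
| 0 | 59% | 9% |
| -0.001 | 73% | 4% |

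The pass rate under the printed rule rises as NPWT gets worse.

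**The case against.** The strongest reply is that nobody would apply these rules so literally. A health economist leads the analysis, the plan commits to recognised guidance, and mean costs and outcomes will be reported beside the ratios, so a dominated result would be visible. The label makes the intended SSI measure clear, its magnitude is unaffected, and no threshold uses it. All of that is fair, and a dominated NPWT would probably be recognised in practice. But a general commitment to guidance does not override an explicit formula and threshold, and a prespecified rule should not rely on unwritten correction.

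A second objection is that judging the cheaper, fewer-QALYs quadrant by net benefit assumes that a QALY lost is valued at the same $100,000 as a QALY gained, which the plan does not say. This stands for the -$400, -0.001 example. It does not rescue the -$10, -0.001 example, where only $10,000 is saved per QALY lost, well below the plan's own value. The costlier, fewer-QALYs case needs no such assumption.

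Third, the cost and QALY differences are invented, and some are remote. Saving $400 with a $500 device needs $900 of offsets per woman; if these came only from the 3-point SSI reduction, that is 900 / 0.03 = $30,000 per SSI avoided. This is correct, and the examples show direction, not likelihood.

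Finally, the two-tailed testing in section 6.1.1, "enabling us to detect an increase or decrease in rates of outcomes with use of prophylactic NPWT", concerns sample size and power. It shows only that the investigators do not rule out harm.

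**Conclusion.** Both defects hold on the printed text. The cost per SSI prevented carries the wrong sign in every case, a swing from +$16,667 to -$16,667 at the design rates and device price, but it decides nothing by itself. The QALY rule is the more serious fault: every result with higher cost and fewer QALYs passes, whatever the amounts. When NPWT is cheaper with fewer QALYs, the rule is inverted relative to net benefit at $100,000, on the assumption that the threshold applies equally to losses. With a positive QALY difference the rule works.

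How often the fault would matter depends on the utility and variance assumptions in Step 3. The damage is confined to Secondary Aim 2. It should be fixed, but it does not threaten the trial's main conclusions.

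**What to change.** 1. In section 6.2.2, change the denominator of the cost per SSI prevented to the standard-care rate minus the NPWT rate. A negative corrected ratio can still mean either dominance or being dominated (compare -$3,333 and -$50,000 in Step 1), so report the cost and SSI differences beside it.
2. Replace the QALY rule in one of two ways. Either define cost-effective as 100,000 x QALY difference - cost difference > 0, or apply the $100,000 threshold only when the QALY difference is positive and state how dominance and the cheaper, fewer-QALYs quadrant are classified.
3. Optionally, name the interval method for the ratio. Its confidence interval can be unbounded when the QALY difference is near zero, so net benefit with a 95% interval and an acceptability curve from the planned simulation would be a useful addition.

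The cost is a few lines in section 6.2.2 or in the separate plan. Section 5.3 says analysis will proceed "in accordance with the analysis plan to be finalized by the steering committee and approved by the DSMB", which gives a natural place for the change. No extra data or patients are required.

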#### *Cost-Effectiveness Analysis*

The economic analysis will be led by [name], MPP, MPH, PhD, an MFM Specialist and Health Economist with extensive experience in cost-effectiveness analysis. We will adhere closely to the guidelines for economic analysis accompanying clinical trials set forth by the international Task Force on Good Research Practices on RCT Cost-Effectiveness Analysis. The primary perspective of this economic evaluation will be societal, but we will also examine the patient and health care payer perspectives. This analysis will follow the intention-to-treat principle. The time horizon for the analysis will be the 30-day follow-up period of the trial, but we will include costs for treatment of SSIs beyond 30 days. Costs and effects will not be discounted because the time horizon for the analysis is short.

**Costs:** Direct medical costs will be the primary measure, but indirect costs may be considered if feasible. Direct medical costs will include the cost of implementing prophylactic NPWT or standard dressing (e.g., device or dressing cost, treatment of side effects), and medical care for SSI (e.g., hospital costs, emergency room, outpatient services, wound care supplies, and medications). Indirect costs will include cost of traveling for outpatient visits and lost productivity from being absent from work or usual activity. Secondary data sources will be used as much as possible to reduce the burden of data collection for economic analysis. Unit costs for inpatient and outpatient services, outpatient procedures, laboratory tests, and office visits will be estimated by using charges adjusted for cost-to-charge ratios. The unit cost of medications will be derived from average wholesale prices. Unit costs for study patients' time will be based on the average national wage rate.

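### The cost-effectiveness criterion puts no condition on the sign of the QALY difference, so read literally it accepts NPWT when NPWT costs more and does worse

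*Combined protocol and SAP*

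**What the plan says.** Secondary Aim 2 (section 1.2) hypothesises that "prophylactic NPWT in obese women at cesarean will be cost-effective". Section 6.2.2 gives the only criterion for judging this: "prophylactic NPWT will be considered cost-effective if the incremental cost per QALY is less than" $100,000. The ratio is signed: mean cost with NPWT minus mean cost with standard care, over mean QALYs with NPWT minus mean QALYs with standard care.

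On uncertainty the same section says "All estimates of costs, outcomes, and cost-effectiveness will be reported as means with 95% confidence intervals", and it adds parameter sensitivity analyses and a Monte Carlo simulation. On the horizon: "The time horizon for the analysis will be the 30-day follow-up period of the trial". Utilities come from the EQ-5D, given at the day-30 call, on a scale where 1 is perfect health and 0 is death.

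No section limits the criterion to a positive QALY difference, says how a dominant or dominated result is to be classified, or uses net benefit.

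**The concern.** A threshold on a signed ratio works only when the denominator is positive. When it is negative, dividing by it reverses the inequality. Every costlier-and-worse result then has a negative ratio, which is below $100,000 and passes.

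The denominator here is near zero by design. Thirty days caps QALYs at a small fraction of a year, and the planned effect is a few percentage points of SSI. Two outputs are at stake: the verdict on Secondary Aim 2, and the 95% confidence interval for the ratio. That interval behaves badly whenever the QALY difference could be zero.

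**Working it through.** **Nothing to reproduce in the rule itself.** The $100,000 threshold is a convention. The sample size, used below only for n, does reproduce: 10% versus 7% at 80% power needs 1356 per arm, 2712 in total, and 2712 / 0.95 = 2855 against the stated 2850.

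**1. Written rule against net benefit.** Let dC and dQ be the NPWT-minus-standard differences in cost and QALYs. The written rule accepts if dC/dQ < 100,000. Incremental net monetary benefit is NMB = 100,000 x dQ - dC, and it accepts if NMB > 0. For dQ > 0 the two are the same. For dQ < 0, dC/dQ < 100,000 means dC > 100,000 x dQ, which is NMB < 0, so the verdict is exactly reversed.

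| dC | dQ | Ratio | Written rule | NMB | NMB verdict |
|---|---|---|---|---|---|
| +$500 | +0.01 | $50,000 | accept | +$500 | accept |
| +$500 | +0.001 | $500,000 | reject | -$400 | reject |
| -$500 | +0.001 | -$500,000 | accept | +$600 | accept |
| +$500 | -0.001 | -$500,000 | accept | -$600 | reject |
| +$500 | -0.01 | -$50,000 | accept | -$1,500 | reject |
| -$50 | -0.001 | $50,000 | accept | -$50 | reject |
| -$500 | -0.001 | $500,000 | reject | +$400 | accept |

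Rows 3 and 4 have the same ratio but opposite meanings. The last two rows (cheaper but worse) also assume that a QALY lost is valued at $100,000, which the plan does not say. The costlier-and-worse rows need no such convention.

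**2. Size of the denominator.** The horizon caps QALYs at 30/365 = 0.0822 per woman. Section 6.1.1 plans for "the difference between a 10% rate of SSI in the standard care group and a 7% rate in the NPWT group". Even if each averted SSI turned 30 days at utility 0 into 30 days at utility 1, the mean gain through SSIs averted would be 0.03 x 30/365 = 0.0025 QALY per woman.

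**3. How often dQ is negative, or its interval includes zero, if QALYs are modelled from SSI rates.** Assumption: a fixed QALY loss per SSI and nothing else. n = 2850 x 0.95 / 2 = 1354 per arm; p0 = 0.10; SE = sqrt[p0(1-p0)/1354 + p1(1-p1)/1354]; z = (p0 - p1)/SE. P(dQ < 0) = Phi(-z). P(95% interval includes zero) = Phi(1.96 - z) - Phi(-1.96 - z).

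| SSI with NPWT | z | dQ negative | Interval includes zero |
|---|---|---|---|
| 7% (planned) | 2.803 | 0.25% | 20% |
| 8% | 1.819 | 3.4% | 56% |
| 9% | 0.888 | 18.7% | 86% |
| 10% (no effect) | 0 | 50% | 95% |

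The 20% is the complement of the plan's own 80% power. In 400,000 simulated trials at 10% versus 7% the two rates were 0.23% and 19.8%.

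**4. The same rates if QALYs come from the day-30 EQ-5D.** The documents give neither a utility SD nor an expected gain, so both are assumed, with the day-30 utility applied to all 30 days. SE = SD x (30/365) x sqrt(2/1354), which is 0.000316 for SD 0.10 and 0.000632 for SD 0.20.
- True gain 0.001, SD 0.10: negative in 0.08%, interval includes zero in 11%.
- True gain 0.0005, SD 0.20: negative in 21%, interval includes zero in 88%.

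These gains are generous. To arise through SSIs averted at the planned rates they need a utility loss of 0.0005/0.00247 = 0.20 to 0.001/0.00247 = 0.41 per SSI, held for 30 days. With assumed losses of 0.05 to 0.20 and the same SDs, dQ is negative in 6% to 42% of trials.

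**5. The interval for the ratio.** By Fieller's method the 95% set for dC/dQ is unbounded exactly when the 95% interval for dQ includes zero. A percentile bootstrap interval would be finite, but it would pool dominant and dominated replicates under the same negative values.

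**6. Threshold applied draw by draw (illustration; inputs assumed).** With dC of mean $300 and SE $50, and dQ of mean 0.00025 and SE 0.00047, the written rule accepts about 30% of draws, nearly all of them dominated. Net benefit accepts 0.003%.

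**The case against.** The strongest reply is that nobody would apply the rule this way. The economic section says "We will adhere closely to the guidelines for economic analysis accompanying clinical trials", a health economist leads the work, and section 5.3 refers to "the analysis plan to be finalized by the steering committee and approved by the DSMB". Section 2.3 says the device must improve clinical outcomes to justify wide use, so the authors plainly did not mean to endorse a costlier, worse device. Signs are used loosely nearby as well: cost per SSI prevented is divided by the NPWT rate minus the standard rate, so a costlier, effective device would show a negative cost. Costs and outcomes are reported separately, so a reader could recognise a dominated result. At the planned effect, on the SSI-modelled reading, a negative QALY estimate is rare (0.25%). The larger percentages concern the interval rather than the verdict, and the plan does not name Fieller's method or say that the threshold is applied to Monte Carlo draws.

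Much of this stands as a limit on the consequences. The EQ-5D rates rest on assumed inputs and should not carry weight by themselves. But none of these statements gives a different rule. The guideline reference is general and the documents quote no decision rule from it; the background text concerns clinical outcomes, not QALYs. Relying on the analyst's judgement means overriding the written criterion once the results are known, which prespecification is meant to prevent.

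**Conclusion.** The concern holds. As written, the sole criterion for Secondary Aim 2 accepts the whole costlier-and-worse quadrant and cannot separate dominated from dominant results. That follows from the formula and needs no assumptions. How often it would bite depends on how QALYs are built and on the true effect: on the SSI-modelled reading, from 0.25% of trials at the planned effect to 50% with none. These are rates of disagreement between the written rule and sample net benefit, not rates of wrong conclusions about the truth. The interval problem is the more likely one: on that reading the QALY interval includes zero in 20% to 95% of trials, and a Fieller interval for the ratio would then be unbounded. The primary analysis, the data collected and the sample size are untouched. This should be fixed before the economic analysis is run.

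**What to change.** In section 6.2.2, or in the analysis plan still to be finalised, replace the criterion with: NPWT is cost-effective if $100,000 x (mean QALY with NPWT - mean QALY with standard care) - (mean cost with NPWT - mean cost with standard care) is above zero, reported with a 95% confidence interval.

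Alternatively, keep the ratio but apply the threshold only when the QALY difference is positive. Report cheaper-and-better results as dominant, and costlier-and-worse results as dominated and not cost-effective. If $100,000 is also meant to apply to QALYs lost when NPWT is cheaper but worse, say so.

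When the QALY interval includes zero, give the interval for net benefit rather than for the ratio. If the threshold is applied to Monte Carlo draws, use the same rule there.

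The cost is one or two sentences and a few lines of code. The data, threshold and sample size stay the same, and no verdict changes when the QALY difference is positive.
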